#### Abstract

Acute intermittent hypoxia (AIH) consists of alternating periods of breathing mildly hypoxic and normoxic air, and is a well-characterized stimulus to serotonin-dependent motor plasticity (1, 2). More than two decades of research from several independent laboratories indicates AIH elicits meaningful respiratory and non-respiratory motor recovery in both animal and human models of health and neurological injury, particularly chronic incomplete spinal cord injuries (3-7). Of particular importance, the "low dose" of intermittent hypoxia represented by AIH is well below that encountered with sleep apnea, and elicits functional benefits in diverse physiological systems without detectable pathology (8, 9).

Our group is interested in the therapeutic potential of AIH for individuals with neuromuscular disease. In preliminary studies on rodent models of amyotrophic lateral sclerosis (ALS), brief AIH exposures restore lost respiratory function. Based on the efficacy of AIH in ALS rats (10, 11), and the success in translating this novel therapy to humans with chronic neurological impairment, the potential benefits of AIH in ALS patients warrant careful investigation. Most ALS patients survive less than 5 years after diagnosis, and the main cause of death is respiratory failure (12, 13). Few options are available to preserve breathing other than mechanical ventilation, which diminishes the quality of life to an extent that it is often rejected by ALS patients. Any treatment options to preserve/prolong independent breathing ability will greatly enhance the quality (and duration) of life in those suffering from ALS. Here, we seek proof of concept data that AIH may be a simple and effective therapeutic option to preserve independent breathing ability in ALS.

The fundamental hypothesis guiding this proposal is that even a single AIH trial improves respiratory (and non-respiratory) motor function in ALS patients. We propose to evaluate respiratory and limb strength, minute ventilation and respiratory muscle EMG activity in ALS patients versus healthy age and sex-matched controls in response to AIH and sham AIH (normoxia) interventions. We will investigate the ability of a single AIH trial to increase voluntary respiratory motor function (Aim 1). An additional, exploratory aim tests the hypothesis that ALS patients utilize distinct patterns of respiratory muscle recruitment versus healthy controls, and that these patterns are partially normalized by AIH (Aim 2). Both aims are designed to collect preliminary safety and feasibility data as we develop methods that improve our ability to detect and treat respiratory impairment in ALS.

#### Background

Acute intermittent hypoxia (AIH) consists of short, repeated presentations of reduced oxygen in the inspired gas (~9-11% oxygen, ~1 – 1.5 minutes), interspersed with normal oxygen periods (~1-1.5 min, inspired  $O_2=21\%$ ). AIH induced motor plasticity was first described more than two decades ago as a persistent enhancement of phrenic and hypoglossal neural activity lasting hours after AIH had ended. (14, 15) Subsequent research demonstrated that AIH preconditioning causes cumulative effects, and enhances the extent of motor facilitation induced by a single AIH presentation (16, 17). These observations triggered investigations concerning the potential of repeated AIH as a treatment to preserve and/or restore breathing ability with neural injury or disease (3, 9).

More than two decades of research on animal models have produced a detailed understanding of mechanisms giving rise to AIH-induced respiratory motor plasticity (3, 4, 6, 18, 19). Briefly, each hypoxic episode activates ventilatory chemoreflexes initiated by carotid body chemoreceptors. Carotid body sensory activity stimulates medullary respiratory neurons that increase breathing (1, 2) and raphe neurons that contain the neuromodulator, serotonin. During each hypoxic episode in the AIH protocol, this neural network is repeatedly activated. The episodic release of serotonin near respiratory motor neurons is at the heart of AIH-induced plasticity versus low oxygen *per se* (4). Episodic activation of serotonin receptors on respiratory motor neurons initiates intracellular signaling cascades that trigger new brain-derived neurotrophic factor (BDNF) protein synthesis, strengthening synapses from medullary respiratory and non-respiratory motor neurons as confirmed in numerous studies in both normal (3, 20, 21) and injury/disease rodent models (3, 22). When AIH is repeated daily for many days-to-weeks, the magnitude and duration of plasticity is amplified (22).

The dose of intermittent hypoxia is critical in determining the direction and extent of plasticity, and the potential for adverse events (8). For example, high doses of intermittent hypoxia simulating obstructive sleep apnea [80 or more episodes per day/night; severe hypoxemia within each episode] elicit pathology, including systemic hypertension, neuroinflammation, and cognitive impairment (23, 24). On the other hand, respiratory motor plasticity is undermined by severe intermittent hypoxia protocols due to neuroinflammation (25). **In striking contrast**, repeated, low dose AIH [<15 episodes per day; modest hypoxemia per episode] elicits neuroplasticity without detectable pathology (26-31). To the contrary, repetitive low dose AIH exerts beneficial effects in multiple organ systems by independent research groups (for review see: (8)).

Here, we propose to study mechanisms of respiratory plasticity associated with a single presentation of mild AIH. AIH is simple to apply and well tolerated by most individuals. In eight studies on humans with chronic spinal cord injury published to date, an AIH protocol similar to that proposed here has not been associated with any adverse events (5, 7, 31-35). Several other completed, but not yet published studies from multiple laboratories increase our collective experience with (and confidence in) this protocol (Christensen et al., submitted; Sandhu et al., in preparation; Ahmed et al., in preparation). All available evidence is consistent with the conclusion that AIH protocols similar to that proposed here are safe in humans, although we do not yet have experience with ALS

#### patients.

Accumulating evidence demonstrates that a similar AIH protocol to that proposed here induces respiratory motor plasticity in humans. For example, in healthy sleeping adults, tidal volume and ventilation acutely increase during each hypoxic episode, and remain above baseline >20 minutes post-AIH (36). Sustained motor facilitation is also observed in genioglossus EMG activity, presumably stabilizing the upper airway (37). Using a slightly different AIH protocol (with a background of mild hypercapnia), prolonged increases in tidal volume (and ventilation) are observed in awake humans with chronic spinal injury (34). In adult patients with chronic incomplete spinal injury, a single, 30minute AIH session (15, 1 min episodes) elicited >80% gain in ankle torque generation and EMG burst amplitude for up to 4 hours post-AIH (7). AIH-induced gains in limb muscle torque correlate with enhanced motor recruitment (5). Here, we propose to study effects of a similar, single AIH session in normal subjects and ALS patients to gain proof of principle that AIH elicits plasticity and meaningful functional benefits in this patient population. Although repeated, daily AIH exposure for 5 days extend the duration of motor enhancement to weeks (35), we do not yet feel justified in exposing ALS patients to such prolonged protocols pending the outcome of these initial experiments.

Based on abundant experience in humans, the AIH protocol proposed here is noninvasive, easy to administer and, importantly, has no history of adverse effects. Further, when people with chronic spinal cord injury are asked which day they had received AIH versus sham normoxia treatment, they are unable to tell (their guess has a 50/50% chance of being correct); thus, AIH at these levels is not stressful (indeed is barely detectable) for those with neurologic injury. The most notable discomfort reported during an AIH protocol is wearing the respiratory mask. Collectively, evidence from both animal models and humans with neurologic injury support the case that AIH is a safe, simple (non-invasive) and effective means of improving both respiratory and non-respiratory motor function, and that it has the potential to at least transiently improve motor function in diverse clinical disorders that compromise movement (9).

Early results (n=6) indicate respiratory motor gains in some, but not all subjects following AIH. While the primary means of AIH motor facilitation occurs via serotonergic signaling, AIH motor facilitation can occur through an alternative, adenosine-mediated signaling pathway (38, 39). The serotonergic and adenosine pathways compete for dominance via cross-inhibition, and when activated equally, they cancel one another (19, 40). However, recent basic science data from our group indicates that pre-treatment with an adenosine receptor antagonist can restore AIH-induced respiratory motor function (41). Aim 3 is an optional/exploratory aim evaluating whether co-administration of lowdose (3 mg/kg) caffeine, a non-selective adenosine receptor antagonist, augments respiratory and grip function to a greater degree than AIH alone. Caffeine is rapidly absorbed, and then degraded to paraxanthine in the liver via Cytochrome P450 1A2 (CYP1A2). Maximal serum concentrations are reached within ~1 hour of consumption.(42) The plasma half-life of caffeine is ~4 hours, but ranges from 2-8 hours between individuals.(43) Caffeine freely crosses the blood-brain barrier and enters the CNS; 3 mg/kg of caffeine inhibits A2A (~60%) and A1 receptors (50%); 6 mg/kg of caffeine yields ~75% A2A and ~65% A1 receptor inhibition.(44) Caffeine also inhibits phosphodiesterase activity, but only at doses >9 mg/kg.(45) Caffeine is the most widely

used psychoactive drug worldwide (46), and is considered safe for use in most neurodegenerative disorders, including ALS (47, 48).

### Preliminary studies in rodent models of ALS:

Diminished breathing ability can be partially restored by harnessing the intrinsic capacity for plasticity (1). In rats with incomplete cervical spinal injury, even a single presentation of AIH increases phrenic/diaphragm function ipsilateral to injury (22, 49). Repetitive AIH for one week enhances both the magnitude and duration of this effect (20, 31, 35). The mechanism of functional recovery is a shifting function of time post-injury; for example, 1 week of daily AIH beginning 1 week post-injury improves breathing capacity by an adenosine dependent, serotonin-independent mechanism (31, 50). On the other hand, 1 week of daily AIH elicits functional improvement of breathing capacity by a serotonin-dependent, adenosine constrained mechanism. Thus, multiple, time-dependent mechanisms can contribute to the functional plasticity observed. Both mechanisms of functional recovery are transient, although prolonged repetitive AIH exposures appear to elicit more robust and prolonged functional recovery. We are currently exploring optimal protocols with respect to both the amplitude and duration of functional improvement.

Preliminary studies demonstrate that even a single AIH exposure restores diminished phrenic nerve activity during late-stage disease in a rat model of ALS, the SOD1G93A transgenic rat (10, 11, 51, 52). Indeed, in end-stage rats, AIH-induced phrenic motor facilitation is nearly double that found in wild-type littermates or in mutant rats during early stage disease (52). In end-stage ALS rats, enhanced AIH-induced phrenic motor facilitation utilizes the same serotonin-dependent mechanisms as in wild-type rats (10). These preliminary data and proof of concept studies in humans with incomplete spinal cord injury provide a strong rationale to evaluate responses to a single session of AIH in patients with ALS. Our initial investigations on a single AIH presentation will guide efforts as we work to evaluate repetitive AIH as a potential therapeutic modality in humans with ALS.

## Our plan:

As a relentlessly progressive neuromuscular disease that leads to paralysis from motor neuron death, any strategy to preserve motor function for as long as possible will greatly impact the quality of life in those suffering from ALS. Current clinical ALS management includes various forms of assisted ventilation (53). However, assisted ventilation atrophies respiratory muscles, further degrading independent breathing ability (54); it takes things in the wrong direction. AIH is a potential therapy to preserve independent breathing ability, delaying the need for assisted ventilation and improving the quality and duration of life for ALS patients. We begin this line of investigation with two, limited specific aims designed to establish proof-of-principle that AIH has the intended effect.

- We will begin investigations of AIH in ALS patients by focusing on a **single AIH session** to establish proof-of-principle before considering more extensive studies of repetitive AIH, which has greater potential to alter the course of disease.
- Since the major cause of death in ALS is ventilatory failure (34), and studies of AIH-induced respiratory motor plasticity led to the principle repeated AIH as a therapeutic modality (9), our initial focus will on AIH and breathing ability in ALS patients.

- We will collect additional preliminary data on limb function (grip strength) since AIH increases strength in several motor systems, potentially benefiting patients.
- Aim 3 (optional aim) will independently evaluate the effect of pre-treatment with caffeine on respiratory and non-respiratory motor performance post-AIH.
- Our goal with this initial project is to collect preliminary data necessary to provide proof-of-concept, and to provide the foundation for extramural grant applications.

## Specific Aims

**Aim 1: Test the hypothesis that a single AIH trial increases maximal respiratory and non-respiratory motor function in ALS.** Dependent variables will include: maximal inspiratory pressure (MIP) and maximal handgrip force (MHGF). We will address the following questions:

- a. Does AIH increase voluntary inspiratory pressure generation?
- b. Does AIH increase maximal handgrip force?
- c. Are baseline MIP and MHGF inversely related to AIH-induced facilitation?

Aim 2: Test the hypothesis that a single AIH trial increases resting respiratory motor function in ALS. Dependent variables will include: resting tidal volume, respiratory EMG at rest, resting ventilatory drive. Three questions will be addressed:

- a. Does AIH increase resting tidal volume?
- b. Does AIH increase the resting ventilatory drive?
- c. Does AIH increase respiratory muscle activation and restore more normal respiratory muscle recruitment patterns?

Aim 3: Test the hypothesis that pre-treatment with caffeine will augment respiratory and non-respiratory motor function. Dependent variables will include: maximal respiratory pressures, maximal grip force, resting tidal volume, EMG. Three questions will be addressed:

- a. Does acute consumption of caffeine enhance AIH-induced facilitation of respiratory and non-respiratory motor function?
- b. Is there a difference in AIH-induced facilitation of respiratory and nonrespiratory motor function between slow and fast caffeine metabolizers?
- c. Does acute consumption of caffeine improve the AIH-induced increase in respiratory muscle activation?

## **Research Plan**

Figure 1: Proposed screening procedures.

**Design:** Subjects will be screened for eligibility on Day 1 (**Figure 1**); those who meet the criteria will continue with the study.

The study design (**Figure 2**) will consist of up to three separate testing sessions, separated by approximately two weeks (+/- 3 days). One session will be a single, ~45-minute AIH protocol. The other will be 45 minutes of Sham AIH (ie. normoxia). Session order will be random. A third, optional session will be offered to eligible subjects (caffeine + AIH). Each session is expected to last ~3 hours, including equipment setup, patient positioning and pressure relief, rest breaks, AIH/Sham AIH, and post-intervention tests.

Subjects who elect to participate in Aim 3 will be scheduled for a third study session consisting of administration of 3 mg/kg of caffeine, followed by AIH 1 hour after caffeine consumption.

Study outcomes in Aim 1 include strength tests (respiratory and handgrip; MIP and MHGF), respiratory drive (P0.1), tidal breathing, and the hypoxic ventilatory response (HVR). In Aim 2, respiratory muscle recruitment will be tested at normoxic rest, during hypoxia, and with maximal voluntary inspiratory pressure generation. Aim 3 outcomes include maximal respiratory pressures, MHGF, tidal breathing, and saliva tests of caffeine metabolism.

Fig 2 Proposed study design.

**Subjects:** We propose to study 18 ALS patients and up to 30 healthy age/sex matched control subjects. Patients who meet study criteria will be identified by [name] (Co-I) through the UF adult neuromuscular clinic. The study PI will screen and consent patients. The PI will review the eligibility criteria. study procedures, participation risks, and the ability of subjects to withdraw from the study at any time.

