Additionally, subjects will be ineligible to participate in Aim 3 (caffeine+AIH) if they: report negative side effects to caffeine consumption (e.g. anxiety, dizziness); have a diagnosis of diabetes (due to effect of caffeine on glucose metabolism (55) or hepatic cirrhosis (impaired metabolism of caffeine (56), or take antiarrhythmic or bronchodilator medications (57).

The sample size is consistent with the time and budget required to acquire strong pilot data for an NIH R01 grant, which is the major goal of this project.

Eligible subjects who agree to participate and sign the informed consent form approved by UF will undergo further screening procedures prior to beginning study procedures. Screening will include a detailed medical and pharmacological history, caffeine consumption questionnaire, forced vital capacity (FVC) testing and resting 3-lead ECG. The likelihood of obstructive sleep apnea will be evaluated using the STOP-BANG questionnaire. Subjects will be informed of their STOP-BANG questionnaire results, and if sleep apnea is suspected, then they will be referred for possible clinical treatment (which is outside of the scope of this study). If they choose to pursue clinical treatment for sleep apnea, then they will be included in the study after 3 months of treatment have elapsed. If they choose not to seek treatment, they will be included in the study. This plan is consistent with recommendations of a recent Intermittent Hypoxia workshop considering the inclusion/exclusion of subjects with sleep apnea; recommendations were made in based on input from two nationally known sleep apnea experts participating in that workshop (Drs. [name], University of Chicago, and [name] at Wayne State University).

At the screening session, subjects who meet all study criteria will be invited to participate in a third study session consisting of caffeine + AIH. Subjects who decline to participate in Aim 3 remain eligible to participate in Aims 1-2.

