### **Statistical Analysis**

The outcomes for both aims are largely quantitative and continuous. Sample distributions and summary statistics will be calculated for each outcome, and non-linear data distributions will be transformed as needed. Study outcomes for Aims 1-2 include acute changes in voluntary strength, resting ventilation, and respiratory drive. Each of these will be evaluated with 3-way repeated measures ANOVAs. Factors will be subject group (patient vs control), AIH condition (AIH vs Sham AIH), and time (pre, 0 minutes post, 30 minutes post, 60 minutes post); Tukey's post hoc test will be used to assess individual differences. A separate ANOVA will compare the independent effect of caffeine on motor function 60 minutes post-AIH. We will work with BERD to use genetic testing results to model independent effects of caffeine metabolism genotype on AIH motor facilitation, as pilot data to estimate sample size for a larger, future project. For the analysis of sEMG Response Vector and Similarity Index, baseline FVC will be used as a covariate. These will be tested with 2-way repeated measures ANOVAs (AIH only, factors: subject group

and time). Relationships between variables will be evaluated with Pearson's correlation. Statistical significance will be p<0.05.

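### Aim 3 compares a caffeine session that, as worded, is always visit 3 and the second AIH exposure, using 60-minute values with no stated baseline adjustment, so the difference cannot be credited to caffeine alone.

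*Combined protocol and SAP*

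**What the plan says.** The Research Plan allows up to three sessions about two weeks apart, plus or minus 3 days. It describes the AIH session, then states: "The other will be 45 minutes of Sham AIH (ie. normoxia). Session order will be random". The caffeine session appears only after that sentence, as an optional extra, and the section continues: "Subjects who elect to participate in Aim 3 will be scheduled for a third study session". The Eligibility Criteria section uses the same description: "At the screening session, subjects who meet all study criteria will be invited to participate in a third study session". The Independent Variable section gives every subject one AIH and one sham session. In the caffeine session, baseline tests come first, then the capsules, then AIH one hour later.

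For the analysis, the Statistical Analysis section says: "A separate ANOVA will compare the independent effect of caffeine on motor function 60 minutes post-AIH". It names no comparator session, change score, baseline covariate, visit term or prior-exposure term for this ANOVA. Specific Aims frames Aim 3 as a hypothesis test and asks whether caffeine enhances the facilitation that AIH induces. Our plan says that caffeine will be evaluated independently.

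Two other statements bear on the comparison. Background says that "AIH preconditioning causes cumulative effects, and enhances the extent of motor facilitation induced by a single AIH presentation". Our plan describes ALS in these terms: "As a relentlessly progressive neuromuscular disease that leads to paralysis from motor neuron death".

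**The concern.** Three things change together between the AIH-alone session and the caffeine session: caffeine is given, the visit number rises to 3, and the subject has already had AIH once. The planned ANOVA would give the whole difference to caffeine.

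The competing influences do not all push the same way. Enhancement by earlier AIH, or practice on effort-dependent tests, would look like a caffeine benefit. Disease progression in patients would hide one. Recruiting more subjects narrows the confidence interval around the mixed quantity without separating its parts. The project is meant to supply pilot data for a larger grant, so a mixed estimate could be used later as if it were a caffeine effect.

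**Working it through.** The documents give no effect size, SD or power for Aim 3, so there is no planned figure to reproduce. The check concerns what the design can estimate.

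**1. Order and timing** (inputs: Research Plan; one interval is 14 ± 3 days)

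| Randomised order | Visit 1 | Visit 2 | Visit 3 | AIH alone to caffeine + AIH |
|---|---|---|---|---|
| AIH first | AIH | Sham | Caffeine + AIH | 2 × 14 = 28 days (2 × 11 = 22 to 2 × 17 = 34) |
| Sham first | Sham | AIH | Caffeine + AIH | 14 days (11 to 17) |

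If the two orders are balanced, the mean gap is (14 + 28)/2 = 21 days.

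**2. What the comparison estimates.** Write one outcome per session as a subject effect + α (any AIH) + γ (caffeine) + π2 or π3 (visit 2 or 3 relative to visit 1) + λ (an AIH session preceded by another AIH session). With balanced orders:

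mean(caffeine + AIH) − mean(AIH alone) = γ + λ + π3 − π2/2.

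The AIH and sham sessions identify α and π2. Nothing separates γ, λ and π3, because all three appear only in the caffeine session. The rank of the design matrix confirms this. The check uses 12 subjects, the planned number of completing patients, as an upper bound for patients:

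| Terms added to subject, AIH and caffeine | Planned order | All six orders, 2 subjects each |
|---|---|---|
| Free visit effects | rank 15 of 16 columns: not estimable | rank 16 of 16: estimable |
| Prior-AIH enhancement | rank 14 of 15: not estimable | rank 15 of 15: estimable |
| Both | rank 15 of 17: not estimable | rank 17 of 17: estimable |

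With all six orders, the variance of the caffeine contrast is 2σ²/12 = 0.167σ², the same as in an unadjusted comparison.

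**3. What a change score removes.** Suppose drift d shifts a subject's strength at a visit, and g is the gain within that session. Then (L + d + g) − (L + d) = g, so drift in level cancels. The baseline in the caffeine session is taken before the capsules, so this works there too. What stays is anything that alters g itself: λ, or a response to AIH that varies with disease stage. Specific Aims asks under Aim 1 whether facilitation is inversely related to baseline strength, so the second possibility cannot be dismissed.

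**4. Illustrative size (assumptions, not in the documents).**

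- *Raw 60-minute levels in patients.* Assume strength declines 1% to 4% per 30 days. At the mean gap, the shift is 1% × 21/30 = 0.7% to 4% × 21/30 = 2.8%. The extremes are 1% × 11/30 = 0.4% and 4% × 34/30 = 4.5%.
- *False attribution.* Assume a non-caffeine shift of k SDs of the paired difference, no caffeine effect, and a two-sided 5% paired t-test (the plan gives p<0.05 but no sidedness). The chance of declaring a caffeine effect comes from the noncentral t distribution with n − 1 df and noncentrality k√n; for n = 12 and k = 0.3, that is 0.3 × √12 = 1.04.

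| Pairs | k = 0.2 | k = 0.3 | k = 0.5 |
|---|---|---|---|
| 6 | 7% | 9% | 17% |
| 12 | 10% | 16% | 35% |
| 32 (12 patients + 20 controls) | 20% | 38% | 78% |

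The last row is the case in which every completing patient and control takes part. The error rate grows with n because the shift does not shrink.

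**The case against.** The strongest reply is that the data needed to deal with drift are already planned. Every session has its own baseline, and the one at visit 3 precedes caffeine. Aim 3 asks about facilitation, which is naturally a within-session gain. A reader might infer that Aim 3 cannot separate caffeine from disease progression and practice at all. The documents do not support that: a change score largely removes drift in level, and the three baselines show how large it was. Healthy controls, who are not excluded from Aim 3, have no ALS progression. The maximal pressure and grip tests are repeated until three readings agree within 10%, which limits learning within a session. What stands against the plan is that the Statistical Analysis section does not say that a change is what will be analysed.

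A reader might also infer that prior AIH is known to enhance the later response here. The documents do not show this either. Background speaks of preconditioning in general, and the title of one of its two references concerns chronic intermittent hypoxia. Elsewhere Background reports effects of a single session for up to 4 hours and links effects lasting weeks to five days of daily exposure. The rodent section calls the recovery mechanisms transient. Persistence of an effect and enhancement of the next response are different things, so enhancement after 11 to 34 days remains possible, but its size is unknown and may be near zero.

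Nor is it true that no visit term could ever help. With a strictly linear trend and no prior-AIH enhancement, caffeine is estimable under the planned order, at 0.542σ² against 0.167σ² (3.25 times the variance). That rests on assumptions the planned order cannot test.

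Finally, keeping an exploratory session last protects the main AIH-versus-sham comparison and is a defensible choice. Background labels Aim 3 optional and exploratory. This limits the consequence but does not support describing the result as an independent caffeine effect.

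**Conclusion.** The point holds in two parts.

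First, the Aim 3 outcome is under-specified. Taken as raw 60-minute levels, it mixes caffeine with between-visit drift: progression in patients and repeat testing in everyone. This is an analysis gap that the planned measurements can largely close.

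Second, even with within-session change, caffeine stays fully aliased with second AIH exposure and with any visit-3 effect on the response to AIH. No sample size and no free visit term resolves this under the planned order.

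The conclusion assumes that the wording gives the order. Figure 2 is not shown, and the sentence on random order could be stretched to cover all three sessions; if that is meant, the protocol should say so. The percentages in the working are illustrations under stated assumptions and do not estimate the actual bias. The change is worth making because it costs little and corrects what Aim 3 can conclude. It does not call Aims 1 and 2 into question.

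**What to change.** 1. **Session order.** State in the Research Plan which sessions are randomised and whether caffeine + AIH is always last.
2. **Outcome.** In the Statistical Analysis section, define the Aim 3 outcome as the change from the same session's pre-caffeine baseline to 60 minutes post-AIH, compared within subject with the same change in the AIH-alone session. Use the baselines at visits 1 to 3 to report between-visit drift, separately for patients and controls. Note as a limit that capsules follow baseline and AIH starts an hour later, so this change spans about an hour more in the caffeine session unless AIH alone has an equal wait, which the documents do not state.
3. **Claim, if the caffeine session stays last.** Replace the reference to an independent caffeine effect in Statistical Analysis, and the matching wording in Our plan and Specific Aims, with an exploratory comparison in which caffeine is confounded with second AIH exposure and visit 3. Do not carry the estimate forward as a caffeine effect.

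These changes cost protocol wording only. The pressure, grip and tidal-breathing baselines and 60-minute tests are already scheduled.

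**Option.** Randomise the order of all three sessions for subjects who accept Aim 3 at screening, with a visit term in the model. This would remove the aliasing without extra visits, but it is a trade-off. In three of the six orders caffeine + AIH precedes AIH alone, and in three it precedes sham. Any enhancement, or dropout after an early caffeine visit, could then affect Aims 1 and 2. It would also leave a separate gap: with no caffeine + sham session or placebo capsule, a direct effect of caffeine on strength could still not be told apart from enhanced AIH facilitation.
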